11. DATA AND SAFETY MONITORING

11.1 Data and Safety Monitoring Plan

- Safety review will take place on site on every follow up visit by the examining physician that will monitor all patients for any complication or side effect from treatment; if serious treatment will be stopped. All adverse events and unanticipated problems will be reported to the Human Studies Committee as previously explained. Every examining physician has the expertise and knowledge to identify any complication from the treatment each patient is receiving. Each physician and member of the study has completed MEEI training. Each month, the study will be assessed by the PI and study coordinator to evaluate for significant adverse or treatment effects. All data collected will be stored in a locked cabinet inside the oculoplastics administrative office.

12. DATA HANDLING, RECORD-KEEPING AND MONITORING

12.1 Data Recording, Record-Keeping and Monitoring

- A Case Report Form (CRF) will be completed for each subject enrolled into the clinical study. The Sponsor-Investigator will review, approve and sign/date each completed CRF; the Sponsor-Investigator's signature serving as attestation of the Sponsor-Investigator's responsibility for ensuring that all clinical data entered on the CRF are complete, accurate and authentic. The physician will review the informed consent, confirm subject eligibility and verify the accuracy of data transfer from the source document to CRF. Data monitoring will occur monthly if new patients have been recruited during that specific time. Data review will be done by PI and study coordinator.
- Source Data are the clinical findings and observations, and test data/measurements, and other information contained in Source Documents. Source Documents are the original records (and certified copies of original records); including, but not limited to, hospital medical records, physician or office charts, physician or nursing notes, pharmacy dispensing records, recorded data from automated instruments, x-rays, etc. When applicable, information recorded on the CRF shall match the Source Data recorded on the Source Documents.
- The electronic data recording data system being used for this clinical research study has not been fully certified as being compliant with the FDA regulations at 21 CFR Part 11 due to the limited scope of this clinical research study.

13. STUDY DISCONTINUATION CRITERIA

13.1 Discontinuation of Individual Research Subjects

- Discontinuation criteria for individual research subjects has been previously addressed under section 5.2 (Withdrawal of subjects due to non-compliance/adherence) and section 9.3 (Withdrawal of subjects due to adverse events) of the clinical protocol. Decision will be done by PI. Data will be collected until subjects are withdrawn. If subjects have already received part of the treatment or withdrawn before treatment has been started then subjects will be replaced using the same eligibility criteria.

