9.3 Withdrawal of Subjects due to Adverse Events

- If subject presents with a serious event from intervention, he/she will be withdrawn from further study intervention and the investigators will evaluate the reason for event. If patient states a minor adverse event patient will continue unless patient wishes to voluntary withdraw.
- A serious event includes a severe allergic reaction to medication causing systemic symptoms of anaphylaxis.
- Data will continue to be collected from the withdrawn subjects, until 12 months after original surgery date, but without further intervention (no more injections) and patient will not be included in the analysis.

Withdrawn subjects from study participation due to an adverse event will not be replaced for a new patient.

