### 10.3 Sample Size Determination

- The plan number of subjects to be enrolled into the clinical study is up to 15 for the treatment group and up to 15 for the placebo group. A total sample size of 20 patients is needed to achieve a 80% power to detect a difference of at least 13.2% less than the control in mean changes in graft size from pre-treatment (2-3 weeks post-operative date) to the last follow up with a standard deviation of 10% (common to both groups) and with a significant level (alpha) of 0.050 using a two-sided two-sample equal-variance t-test. If we take into account a 20% dropout rate out of 20 patients, then 12 patients are needed to be enrolled into each arm of the study. For that reason, 15 patients are going to be enrolled but statistical analysis can be done once 10 patients in each arm have completed the study. Determined with the help of [name] at MGH biostatistics department.

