### 10.4 Analysis Population (if applicable)

- Independent sample t-test will be applied to the primary outcome analysis (i.e., comparison of mean changes in graft size from pre-treatment to the last follow up). In addition, for the secondary outcome we will utilize repeatedly measured POSAS scores over time by using longitudinal linear mixed effects model which can further determine the time dependency of the treatment effect. The model will include treatment group (group 0 for placebo and 1 for treatment), time (0=two-three weeks post-op visit / first injection, 1=second injection, 2=third injection, 3=fourth injection, 4=two to three weeks after last injection), and group x time. Both effects (1. group difference in the pre-treatment measurement 2. time trend of the control) will be considered fixed effects and the individual 2-3 weeks post-operative measurement random. Group x time effect is expected to be an increased slope of the treatment group over time. For the other outcome measurements, we will apply the same methods. Also statistical methods will include intention to treat (ITT) analysis to compare all subjects in the groups randomly assigned. We will exclude anyone who gets partial treatment, exit early or is lost to follow up; in those cases we will replace patient with another subject that meets the criteria. Discussed with [name] at MGH biostatistics.

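### Protocol 9.3 and 13.1 disagree on follow-up after an adverse-event withdrawal and, with the exclusions in 9.3 and SAP 10.4, rule out the promised intention-to-treat comparison

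*Protocol*

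**What the plan says.** Four places govern what happens to a withdrawn patient's data.

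- **Protocol 9.3 (adverse-event withdrawals):** "Data will continue to be collected from the withdrawn subjects, until 12 months after original surgery date". No more injections are given. The same sentence leaves the patient out of the analysis, and the section adds that such patients are not replaced.
- **Protocol 13.1 (individual discontinuation):** it refers to both 5.2 and 9.3 for the criteria, then states "Data will be collected until subjects are withdrawn". Subjects withdrawn before treatment or after part of it are replaced.
- **Protocol 5.2 (non-compliance):** patients who do not follow post-operative instructions or miss follow-up appointments are withdrawn and replaced. Nothing is said about later data.
- **SAP 10.4:** the methods will include "intention to treat (ITT) analysis to compare all subjects in the groups randomly assigned". The next sentence excludes and replaces anyone with partial treatment, early exit or loss to follow-up.

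The primary comparison in SAP 10.3 and 10.4 is the mean change in graft size from pre-treatment to the last follow-up. That visit is not defined. The last scheduled visit, in Protocol 7.5 and 7.8, is 12 months after surgery. Neither document gives a method for missing outcomes.

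**The concern.** Site staff cannot follow 9.3 and 13.1 together for a patient withdrawn because of an adverse event: one section keeps measuring the graft and the other stops. Whichever they follow, the patient does not reach the analysis, because 9.3 and SAP 10.4 both remove such patients. An ITT comparison needs the outcome of everyone randomised, and needs those patients kept in their assigned arm. The plan provides neither.

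The stake is bias more than lost numbers. Protocol 9.1 counts graft shrinkage, graft rejection and the need for further surgery among the possible adverse events, and shrinkage is also the primary endpoint. Protocol 9.3 lets a patient with a minor event leave voluntarily. A patient who leaves because the graft is contracting could therefore drop out of the comparison that is meant to measure contraction. Replacing that patient restores the count but does not remove the selection. Measurements not taken after withdrawal cannot be recovered later.

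**Working it through.** **1. The rules side by side**

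| Withdrawn patient | Later data | In the analysis? | Replaced? |
|---|---|---|---|
| Adverse event, 9.3 | Yes, to 12 months | No | No |
| Adverse event, 13.1 | No | Not stated | Yes, if untreated or partly treated |
| Non-compliance, 5.2 with 13.1 | No (13.1) | Not stated | Yes |
| Partial treatment, early exit or lost, SAP 10.4 | Not stated | No, although ITT is promised | Yes |

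The direct conflict over data collection is in the first two rows. The conflict with ITT runs through all four.

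**2. The plan's own sample size.** SAP 10.3: "A total sample size of 20 patients is needed to achieve a 80% power", and "to detect a difference of at least 13.2% less than the control in mean changes in graft size". The SD is 10% in both groups, and the test is a two-sided two-sample t-test at 0.050. Taking difference and SD on the same percentage-point scale, the standardised difference is 13.2 / 10 = 1.32.
- Normal approximation: n per arm = 2 × (1.960 + 0.842)² / 1.32² = 9.01, rounded up to 10.
- Exact t-test: 10.07 per arm, with power 79.7% at 10 per arm.

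The stated total of 20 reproduces.

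**3. Dropout.** SAP 10.3: "If we take into account a 20% dropout rate out of 20 patients, then 12 patients are needed to be enrolled into each arm". The figure of 12 is 10 × 1.20; dividing instead gives 10 / 0.80 = 12.5, or 13. Planned enrolment of up to 15 per arm covers both.

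**4. Patients affected.** Applying the 20% to all 30 planned patients gives 0.20 × 30 = 6, leaving 24, or 12 per arm. Applied to 24 enrolled patients it gives 4.8, about 5. Six is an upper figure, because the 20% is all-cause dropout.

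**5. Power is not the problem.** With 12 completers per arm the exact power is 87.1%.

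**6. Possible bias.** Let the completers in an arm have mean change m, and let a missing fraction f have mean m + d. The full-arm mean is (1 − f) × m + f × (m + d) = m + f × d, so the completers' mean is off by f × d. The documents give no value for d; 5 to 20 points is an assumption.
- f = 0.20, d = 5: 1 point.
- f = 0.20, d = 10: 2 points.
- f = 0.20, d = 20: 4 points.

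The bias in the treatment difference is the bias in one arm minus the bias in the other. It reaches 1 to 4 points only if the selection is confined to one arm, and it cancels if both arms lose the same fraction with the same d.

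**7. Scale.** With 12 completers per arm, the standard error of the difference is 10 × √(2/12) = 4.1 points. A bias of 1 to 4 points is about a quarter of a standard error to one standard error, and 8% to 30% of the 13.2-point target (1/13.2 and 4/13.2).

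**The case against.** The strongest reply is that 13.1 is not the main obstacle to ITT. The exclusion sentence in SAP 10.4 would defeat it even with complete follow-up. That stands, and it is why repairing 13.1 alone would not be enough.

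A second reply is that the sections can be partly reconciled: 9.3 first speaks of stopping the intervention, 5.2 of leaving the study, so each could have its own rule. This is possible but not secure, because 13.1 cites 9.3 by name and 9.3 later speaks of withdrawal from participation.

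Three stronger inferences are tempting, and the documents do not support them.

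- **That many patients would lose the primary outcome.** The direct conflict concerns adverse-event withdrawals only. Protocol 9.3 requires withdrawal only for a serious event, and 9.1 expects none. For non-compliance withdrawals nothing contradicts 13.1, and new wording cannot recover visits that a patient does not attend.
- **That a 12-month primary outcome would be missing.** The SAP names the last follow-up, not month 12. If that means the last available visit, a patient withdrawn after a post-injection visit has a value, though an early one that is not comparable with a 12-month value.
- **That the missingness depends on arm and outcome.** It may, but nothing in the documents shows it, and the trial is double-masked.

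**Conclusion.** The point holds as a contradiction between sections with a consequence for the analysis. Protocol 9.3 and 13.1 conflict on data collection after an adverse-event withdrawal. Together with the exclusions in 9.3 and SAP 10.4, they leave the promised ITT comparison impossible to carry out. The textual conflict is certain.

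The size is less certain. At most about 6 of 30 patients are affected, if the plan's 20% dropout is applied to full enrolment and every dropout counts. The 1 to 4 point shift in one arm's mean rests on an assumed 5 to 20 point difference between missing and remaining patients, with no offset in the other arm. The stated sample size is not in question. The plan should be changed before these outcomes are lost.

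**What to change.** 1. **Protocol 9.3 and 13.1:** use one rule in both. Patients who stop injections or are withdrawn for any reason continue graft measurement, POSAS and safety visits through 12 months, unless they withdraw consent.
2. **Exclusions:** delete the clause in 9.3 that leaves adverse-event withdrawals out of the analysis, and the exclusion sentence in SAP 10.4. State that all randomised patients are analysed in their assigned arm.
3. **Replacement:** reconcile 5.2, 9.3, 13.1 and SAP 10.4. Any replacement is an additional patient and does not remove the withdrawn one from the ITT set.
4. **Endpoint:** define the last follow-up in SAP 10.3 and 10.4 as the 12-month visit.
5. **Missing outcomes:** analyse the repeated graft measurements with a mixed model, so that a patient's earlier visits contribute. SAP 10.4 already describes such a model for POSAS, but its time coding stops 2-3 weeks after the last injection and would have to include the 6- and 12-month visits. Add a sensitivity analysis in which the missing outcomes of one arm are shifted, for example by the 5 to 20 points used above.

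The cost is a SAP amendment as well as protocol wording, plus some extra follow-up and analysis work. The 6- and 12-month visits are already scheduled, and 9.3 already foresees follow-up without injections. No dose, injection schedule or stopping rule changes.

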13.2 Sponsor-Investigator Discontinuation of the Clinical Research Study

- Clinical research study will be discontinued if treatment is showed during the course of the study to be harmful to the patient or graft. The rest of subjects will be notified and evaluated to make sure harmful side effects have not occurred to them.
- The HSC and the FDA will be notified promptly of discontinuation of the entire clinical study.

## 10. STATISTICAL METHODS/DATA ANALYSIS

---

### 10.1 Primary endpoint or outcome measure

- The primary endpoint will be graft size change. Graft shrinkage will be evaluated by measuring the graft before and after surgery (at each post-operative visit) to estimate the contraction with or without treatment.

### 10.2 Secondary endpoints or outcome measure(s)

- The secondary endpoints that will be measured during the clinical study are patient and surgeon satisfaction using the scar assessment scale (POSAS) developed and previously published by Draaijers et al., treatment related adverse events, and early post-operative complications.

### 10.3 Sample Size Determination

- The plan number of subjects to be enrolled into the clinical study is up to 15 for the treatment group and up to 15 for the placebo group. A total sample size of 20 patients is needed to achieve a 80% power to detect a difference of at least 13.2% less than the control in mean changes in graft size from pre-treatment (2-3 weeks post-operative date) to the last follow up with a standard deviation of 10% (common to both groups) and with a significant level (alpha) of 0.050 using a two-sided two-sample equal-variance t-test. If we take into account a 20% dropout rate out of 20 patients, then 12 patients are needed to be enrolled into each arm of the study. For that reason, 15 patients are going to be enrolled but statistical analysis can be done once 10 patients in each arm have completed the study. Determined with the help of [name] at MGH biostatistics department.

### 10.4 Analysis Population (if applicable)

- Independent sample t-test will be applied to the primary outcome analysis (i.e., comparison of mean changes in graft size from pre-treatment to the last follow up). In addition, for the secondary outcome we will utilize repeatedly measured POSAS scores over time by using longitudinal linear mixed effects model which can further determine the time dependency of the treatment effect. The model will include treatment group (group 0 for placebo and 1 for treatment), time (0=two-three weeks post-op visit / first injection, 1=second injection, 2=third injection, 3=fourth injection, 4=two to three weeks after last injection), and group x time. Both effects (1. group difference in the pre-treatment measurement 2. time trend of the control) will be considered fixed effects and the individual 2-3 weeks post-operative measurement random. Group x time effect is expected to be an increased slope of the treatment group over time. For the other outcome measurements, we will apply the same methods. Also statistical methods will include intention to treat (ITT) analysis to compare all subjects in the groups randomly assigned. We will exclude anyone who gets partial treatment, exit early or is lost to follow up; in those cases we will replace patient with another subject that meets the criteria. Discussed with [name] at MGH biostatistics.

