5. STUDY DRUG(S)/DEVICE(S)

5.1 Study Drug Information

- Study drug that will be administered to fifteen of our patients is 5-Fluorouracil, FDA-approved systemic chemotherapy medication to treat certain cancers, the concentration 50 mg/ml and will inject less than 1cc total in the subcutaneous tissue of the affected area.
- Study placebo that will be administered to the other fifteen of our patients is sodium chloride 0.9% (PF).
- Medications will be given every 2 to 3 weeks for a total of 4 injections.
- The amount of medication injected will depend on the extension/dimension of the periocular area affected with a maximum dose of 1cc total.

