8.2 Effectiveness Assessments

- Effectiveness of the study medication will be evaluated by measuring skin graft in each visit after surgery. The measurements will be recorded and analyzed at the end of the study to evaluate the graft size change during the whole study and compare the two groups. Photos will be taken also to objectively observe and document changes. Scar assessment will be evaluated with the use of a questionnaire completed by the observer/surgeon and patient. Questionnaire will be stored and at the end of the study values will be analyzed.

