#### **10.5 Effectiveness Analysis (if applicable)**

- As described above, the population analysis that will be employed in the primary and secondary endpoints is a sample t-test with a level of significance of 0.050.

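### The primary t-test of change does not use pre-injection graft size as a covariate; prespecifying that adjustment, and the scale of change, would be a cheap improvement

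*SAP*

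**What the plan says.** SAP 10.4 fixes the primary analysis: "Independent sample t-test will be applied to the primary outcome analysis", explained there as a "comparison of mean changes in graft size from pre-treatment to the last follow up". SAP 10.5 repeats the choice: "the population analysis that will be employed in the primary and secondary endpoints is a sample t-test with a level of significance of 0.050". The sample size in SAP 10.3 rests on the same test, "using a two-sided two-sample equal-variance t-test", and places the pre-treatment measurement at 2-3 weeks after surgery, the visit of the first injection. None of these sections names a covariate for graft size.

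The starting value will be available. Protocol 8.2 says "Effectiveness of the study medication will be evaluated by measuring skin graft in each visit after surgery", and SAP 10.1 also plans graft measurement at each post-operative visit.

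The only model with a pre-treatment term is the mixed model that SAP 10.4 describes for POSAS. That section adds that other outcomes will be handled by the same methods, but graft size already has its own named test in both 10.4 and 10.5. Protocol 3.2 and 3.2.1 leave randomisation to the pharmacy and describe no stratification by graft size.

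The SAP gives the target difference (13.2%) and the standard deviation (10%) as percentages. It does not say whether change is absolute or relative to the starting size.

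**The concern.** Subtracting the starting value removes all of its influence only if change is unrelated to starting size. If larger grafts contract by a different proportion than smaller ones, part of the spread in the outcome is predictable from a number already on the case report form. An unadjusted test leaves that part in the error term.

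There are reasons to think about size in this trial. Any ocular pathology needing a full-thickness graft is eligible (Protocol 4.1), so sizes may differ a good deal. Protocol 5.1 also ties exposure to size: "The amount of medication injected will depend on the extension/dimension of the periocular area affected", up to a 1 cc maximum. The documents contain no graft-size data, so neither the spread of sizes nor any link with contraction is shown.

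Two things are at stake: some precision, and how well the result stands up if one arm happens to start with larger grafts. With arms this small, a visible imbalance is a realistic prospect. An adjustment chosen after seeing it would carry little weight, so the decision belongs in the SAP.

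**Working it through.** **Inputs.** From SAP 10.3: difference 13.2, SD 10, two-sided alpha 0.05, equal-variance t-test, analysis allowed once 10 per arm have completed, up to 15 per arm enrolled. Both percentages are read as points of percent change. The correlation r between change and pre-injection size is not in the documents. It is an assumption, shown from 0 to 0.5.

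**Step 1: the plan's own figure.** SAP 10.3 says "A total sample size of 20 patients is needed to achieve a 80% power". At n = 10 per arm the standard error of the difference is 10 × √(2/10) = 4.47. The noncentrality is 13.2 / 4.47 = 2.95 on 18 degrees of freedom, and exact power is 79.7%. The stated size reproduces. At 15 per arm the standard error is 10 × √(2/15) = 3.65 and power is 93.7%.

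**Step 2: power with one covariate.** Adjustment reduces the residual SD to 10 × √(1 − r²). It uses one more degree of freedom (2n − 3) and multiplies the variance by 1 + 1/(2n − 4) to allow for chance imbalance in the covariate.

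Example at n = 10, r = 0.5: residual SD 8.66; × √1.0625 = 8.93; standard error 8.93 × √(2/10) = 3.99; power 87.6%.
Example at n = 10, r = 0: 10 × √1.0625 = 10.31; standard error 4.61; power 77.0%.

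| r (assumed) | residual SD | adjusted power, 10 per arm | adjusted power, 15 per arm |
|---|---|---|---|
| 0 | 10.00 | 77.0% | 92.8% |
| 0.2 | 9.80 | 78.6% | 93.7% |
| 0.3 | 9.54 | 80.7% | 94.8% |
| 0.4 | 9.17 | 83.7% | 96.2% |
| 0.5 | 8.66 | 87.6% | 97.7% |
| *t-test, any r* | *10.00* | *79.7%* | *93.7%* |

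Break-even at 10 per arm is near r = 0.25. Simulation with 20,000 trials per setting agrees: at 10 per arm, adjusted power is 77.2%, 81.2% and 87.7% for r = 0, 0.3 and 0.5.

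**Step 3: validity of the planned test.** In the same simulations the type I error of the t-test was 4.8% to 5.1% for every r tried (0 to 0.7).

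**Step 4: chance imbalance.** The difference in mean starting size between arms has standard error √(2/n) in SD units: 0.45 at 10 per arm and 0.37 at 15. The chance of a gap above 0.5 SD is 2 × (1 − Φ(0.5/√(2/n))), which is 26% at 10 per arm and 17% at 15. A 0.5 SD gap moves the unadjusted difference by r × 10 × 0.5:

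- r = 0: no shift;
- r = 0.3: 1.5 points (1.5/13.2 = 11% of the target);
- r = 0.5: 2.5 points (2.5/13.2 = 19% of the target).

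At 10 per arm, given a 0.5 SD gap against the drug, simulated power is 74% unadjusted and 78% adjusted at r = 0.2. At r = 0.5 it is 63% and 87%.

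**The case against.** A reader might infer that the planned test ignores starting graft size, or that chance imbalance makes it wrong. The documents do not support that. The outcome is a change from the pre-treatment value, so starting size is subtracted. If change is a percentage, as the 13.2% and 10% figures suggest, it is also divided by starting size, which removes the obvious proportional link. Chance imbalance is already part of the standard error, and the type I error is correct. The shift of 1.5 to 2.5 points is 0.34 to 0.56 of the 4.47-point standard error, and it needs both a sizeable imbalance and a moderate r.

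A second inference would be that the trial has no room to absorb the loss. SAP 10.3 needs 10 per arm and plans up to 15, at which the t-test already has 94% power.

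It is also fair to say that:

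- nothing in the documents points to r of 0.3 or more, and below about 0.25 adjustment loses a little power at 10 per arm;
- the dose-volume rule is a weak argument for a main-effect covariate. Scaling volume to area may even out exposure, and any remaining interaction of size with drug would arise only in the active arm, which such a covariate does not model;
- regressing percent change on log size does not take baseline measurement error out of the outcome.

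All of this stands and limits the point to efficiency and robustness. It does not remove the case for deciding in advance: at 10 per arm the possible loss is about 3 points of power, while the possible gain is about 8 points at r = 0.5 and larger when an imbalance occurs.

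**Conclusion.** The point holds as an improvement to a valid plan. The primary analysis leaves a planned, pre-injection measurement unused as a covariate at 10 to 15 patients per arm. Relative to the t-test, adjustment changes power by −3 to +8 points at 10 per arm (r = 0 to 0.5), and by −1 to +4 points at 15 per arm. It also protects the estimate against a 0.5 SD imbalance, which arises in 26% of trials at 10 per arm and 17% at 15.

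These figures rest on reading 13.2% and 10% as points of percent change, on a linear relation with a common slope in the two arms, and on an assumed r. If change is absolute, both the power figures and the form of the covariate need to be reconsidered, so the scale should be settled first.

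**What to change.** Before unmasking, amend SAP 10.4 and 10.5 as follows:

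- define the primary variable as percent change in graft size from the 2-3 week pre-injection measurement to the last follow-up, if that is what the sponsor intends;
- make the primary analysis a linear regression of that change on treatment arm, with log pre-injection graft size as the single prespecified covariate;
- report the adjusted difference between arms with its 95% confidence interval;
- keep the unadjusted t-test as a supporting analysis.

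No new data, visits or patients are needed. The cost is one degree of freedom: up to about 3 points of power at 10 per arm, or 1 point at 15, if r is near 0. If r is 0 to 0.2, reaching 80% power takes 11 per arm instead of 10. The planned enrolment of up to 15 covers this, but analysing as soon as 10 per arm have completed would fall slightly short (77% to 79%).
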